## **8. PRESTUDY AND CONCOMITANT THERAPY**

Prestudy therapies administered up to 30 days before first dose of study drug must be recorded at screening.

Concomitant therapies must be recorded throughout the study beginning with start of the first dose of study drug through the Final Study Visit/Safety Follow-up Visit. Medications that are part of the SOC should be recorded as concomitant medications throughout the study. Concomitant therapies should also be recorded beyond Final Study Visit/Safety Follow-up Visit if in conjunction with SAEs that meet the criteria outlined in Section 12.3.2. Serious Adverse Events.

To avoid the confounding effects of antipyretic medications, temperature measurements must be taken, whenever possible, at least 4 hours after administration of the antipyretic medication.

All therapies (prescription or over-the-counter medications, including vaccines, vitamins, herbal supplements; non-pharmacologic therapies such as electrical stimulation, acupuncture, special diets, exercise regimens) different from the study drug must be recorded in the eCRF. Recorded information will include a description of the type of the drug, treatment period, dosing regimen, route of administration, and its indication.

The following pre-study and concomitant therapies are disallowed:

1. More than 1 dose of influenza antiviral medication (eg, OST, zanamivir), or ribavirin within 2 weeks, prior to first study drug intake.
2. IV peramivir more than 1 day prior to screening.
3. An investigational drug (including investigational vaccines) or an invasive investigational medical device within 30 days, or an investigational biological product within 3 months or 5 half-lives (whichever is longer) prior to the first dose of study drug until the end of the study.
4. Use of a live attenuated intranasal spray influenza vaccine within 3 weeks before study entry.

Substrates of OATP1B1 and/or OATP1B3, including atrasentan, bosentan, ezetimibe, glyburide, irinotecan, repaglinide, rifampin, telmisartan, valsartan, and olmesartan may be continued. Statins (ie, 3-hydroxy-3-methylglutaryl-coenzyme A [HMG CoA] reductase inhibitors) may also be continued, but subjects should be cautioned and observed for potential statin-related toxicity.

The sponsor must be notified in advance (or as soon as possible thereafter) of any instances in which prohibited therapies are administered.

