
Incidence of treatment-emergent adjudicated influenza complications including hospitalization
	
The incidence of treatment-emergent adjudicated influenza complications from first intake of study drug until the end of the study or hospitalization 28 days after treatment initiation as defined above.
 
Categories will be Yes (1) or No (0).

Time to resolution of fever (hours) [Time-to event]
	
It is assumed that all subjects will have fever at baseline.
 
The time to resolution of fever is defined as the time in hours from initiation of study treatment to the first of a successive series of 3 recordings for which the fever is resolved (see Table 8). The 3 successive recording may have been done over 4 scheduled successive analysis timepoints, in case of 1 missing in between timepoint.
 
In case the resolution of fever is not achieved, data will be censored.
 
Censoring will be done as follows:
 
 1) Last non-missing record(s) indicate resolution of fever (but insufficient recordings to meet the time to resolution) 
Censoring will be done at the first record of resolution of fever from the last series of recordings of resolution of fever
 2) Last non-missing record does not indicate resolution of fever 
Censoring will be done after the last observation, which is 08:00 on the same day if the last observation was a diary entry from 00:01 until 02:00, 20:00 on the same day if the last observation was a diary entry from 02:01 until 14:00, and 08:00 the next day if the last entry was a diary entry from 14:01 until 00:00.
 
Additionally, in the following cases the subject will be censored using a time-to equal to the maximum time across all subjects:
 
 ○ death, ○ if a subject had not resolved the fever at time of hospitalization and/or during hospitalization and no further data on fever resolution is available

Table 8: Resolution criterion for fever

Assessment	Resolution Criterion
Temperature	temperature as recorded on the ePRO device <37.0°C without the use of antipyretics on that day

The following ATC level 4 codes and generic medication names indicate an antipyretic medication:

- N02BA
- N02BE
- Ibuprofen
- Paracetamol
- Acetylsalicylic acid

If an antipyretic medication misses components of its start and/or stop dates (day and/or month and/or year) the following actions will be taken:

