1. In case of partial start date

- If the day is missing, then the day will be the first day of the month (or the day of first dose whichever is later)
- If the month is missing the month will be January (or the months of first dose whichever is later)
- If the year is missing, then the year will be the year of first dose

2. In case of partial end date

- If the day is missing, then the day will be the last day of the month (or the day of last contact with the subject whichever is earlier)
- If the month is missing, then the month will be December (or the month of last contact with the subject whichever is earlier)
- If the year is missing, then the year will be the year from the date of last contact with the subject.

3. In case of a completely missing start date, the antipyretic will be considered as having started before the trial

4. In case of a completely missing end date, the antipyretic medication will be considered as ongoing at the end of the trial.

Antipyretic medication use associated with both the morning and evening temperature recordings for a particular day is also obtained

	from the subject's diary. If a subject indicates that they used an antipyretic 'today' then the date of this assessment indicates antipyretic use on that whole day. If a subject indicates that they used an antipyretic 'yesterday' then this indicates antipyretic medication use on the whole day before the assessment day.
Incidence of all-cause mortality	Did the subject die after first dose of study drug? Categories will be Yes (1) or No (0).

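### For fever resolution, no rule lets an antipyretic-free diary day clear a day inside a recorded or imputed medication interval, so an open-ended record from Day 1 blocks the event and an over-long one delays it

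*SAP*

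**What the plan says.** SAP 5.3.1.3, Table 8, defines a resolved recording as "temperature as recorded on the ePRO device <37.0°C without the use of antipyretics on that day". The event time is the "first of a successive series of 3 recordings for which the fever is resolved", with one missing timepoint tolerated in between. The Time and Events Schedule of the protocol has subjects record temperature twice daily from Day 1 to Day 14.

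Antipyretic use comes from two sources:

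- **Medication records**, selected by ATC code or generic name. The SAP repairs incomplete dates: "If an antipyretic medication misses components of its start and/or stop dates (day and/or month and/or year) the following actions will be taken". For the stop date, "If the day is missing, then the day will be the last day of the month", or the day of last contact if that is earlier. For a record with no stop date, "In case of a completely missing end date, the antipyretic medication will be considered as ongoing at the end of the trial". For a record with no start date, "In case of a completely missing start date, the antipyretic will be considered as having started before the trial".
- **The diary**, which the SAP brings in as an additional source. It works by whole days: "If a subject indicates that they used an antipyretic 'today' then the date of this assessment indicates antipyretic use on that whole day". An answer of yesterday flags the whole previous day.

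The SAP does not say which source prevails when they disagree. Protocol Section 8 describes the medication entry: "Recorded information will include a description of the type of the drug, treatment period, dosing regimen, route of administration, and its indication". It does not say how as-needed use is to be entered.

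**The concern.** Both protocol and SAP define the endpoint by actual use: a normal temperature for 24 hours without antipyretics. The diary measures use day by day, alongside the temperature. A medication record gives a period, and the stop-date repairs extend that period as far as they can. With the sources added together and no precedence rule, the coarser source can overrule the finer one but not the reverse. A subject who took paracetamol early and then stopped can be counted as treated on later days when the diary reports no intake.

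Such subjects resolve late or are censored around Day 14-15. Median times rise in both arms, events are lost and a treatment difference is diluted, in an endpoint that Protocol Amendment 1 added on Health Authority feedback. No sensitivity analysis of the antipyretic rule is planned. The only extra analysis specific to this endpoint (SAP 5.3.2.3) is the baseline-fever subgroup.

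**Working it through.** The plan gives no figure to reproduce, so the rule itself was applied and then its effect illustrated.

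**1. Applying the rule.** Inputs from the documents: 2 recordings x 14 days = 28 recordings; three successive resolved recordings needed; whole-day antipyretic flag. Assumptions: no missing recordings, and afebrile from the morning of a given day. A recording is resolved if the subject is afebrile and the day lies outside the flagged interval.

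*Stop date missing:*
- Record starts on or before Day 1: all 28 recordings are flagged and resolution is impossible.
- Afebrile from Day 3, record starts Day 5 or later: Day 3 morning, Day 3 evening and Day 4 morning qualify, so resolution is Day 3 morning.
- Afebrile from Day 3, record starts Day 4 or earlier: at most two recordings qualify before the flag, so resolution is never reached.
- Over all combinations of afebrile from Day 1-12 and start on Day 1-14 (12 x 14 = 168), 90 are blocked. The grid is unweighted and is not an estimate of frequency.

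*Closed interval from Day 1, afebrile from Day 3:*

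| Interval | Resolution |
|---|---|
| Day 1-4 | Day 5 |
| Day 1-7 | Day 8 |
| Day 1-12 | Day 13 |
| Day 1-13 or longer | not reached (at most two recordings left) |

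*Stop day missing, month known.* In a 31-day month with first dose on date d, month end is study Day 31 - d + 1. Take a record running from Day 1 with its stop in that month. A first dose on the 25th gives Day 7, a delay to Day 8. A first dose on the 10th gives Day 22, which blocks resolution.

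*Same subject, three derivations.* Assume intake on Days 1, 2 and 5, and afebrile from Day 3:
- Diary alone: resolves Day 3 morning.
- One interval, Day 1-5: resolves Day 6 morning, 3 days later.
- Same record, stop date missing: never resolves.

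**2. Illustrating the size.** Every input here is an assumption: 300 per arm, control median 60 h, 20% shorter on drug (60 x 0.8 = 48 h), log-logistic scale 0.8, times rounded up to 12 h, censoring at 14 x 24 = 336 h, Gehan-Wilcoxon test. A random fraction of subjects is flagged in both arms. Blocked subjects are censored at 336 h. Delayed subjects resolve no earlier than the end of the interval (96 h for Day 1-4, 168 h for Day 1-7). Ranges are across repeated simulation runs.

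| Flagged | Blocked | Delayed, Day 1-4 | Delayed, Day 1-7 |
|---|---|---|---|
| 0% | 50-52% | - | - |
| 10% | 37-44% | - | - |
| 20% | 25-29% | 41-42% | 35-37% |
| 30% | 18-21% | about 40% | about 32% |

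Entries are power. The control median, 66-67 h with none flagged, rises to about 97-98 h with 20% blocked.

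**The case against.** A reader might infer that any as-needed interval or missing stop date marks every day as treated, so that the fever can never resolve. The documents do not support that. A closed interval flags only its own days and usually delays resolution. With a missing stop date, resolution before the record's start still counts. Only an open-ended record starting by Day 1, or an interval running to about Day 13, blocks the event whatever the temperature. This limit stands in full.

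It can also be said that the mechanism is partly assumed. The protocol does not say that as-needed use is logged as one interval, and separate dated entries may be possible. Protocol 17.5 and 17.6 provide for queries and completeness review, so missing stop dates may be rare, and a blank may mean use that truly continued. That stands too: frequency is unknown. It is likewise an inference, though a natural one, that the two sources are additive. The text says the diary is used as well and stops there.

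Finally, counting any documented use is a conservative, pre-specified reading of the protocol definition. The rule is the same in both arms of a double-blind trial, and completely missing dates are handled as in SAP 4.6. This carries less weight. In SAP 4.6 the rule only sorts medications into prior and concomitant, where over-inclusion does little harm. Here it decides whether an event occurs. Equal application gives no evident direction of bias, but it does not prevent dilution.

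**Conclusion.** The concern holds in a limited form. As written, SAP 5.3.1.3 lets a recorded or imputed medication interval overrule a diary that shows no antipyretic use. It prevents resolution when an open-ended record starts by Day 1, and delays it when a closed interval covers days without intake. That much follows from the rules, on the additive reading of the two sources.

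The size does not follow from the documents. It depends on how many subjects have such records and on how as-needed use is entered, and neither is given. With the assumed inputs and 20% flagged, power falls from about 50% to 25-29% under full blocking, or to 35-42% under delay by a Day 1-7 or Day 1-4 interval. These figures describe sensitivity to the rule and do not forecast this trial.

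The endpoint is secondary and outside the hierarchy in SAP 5.1.1, so the primary analysis and the two tested secondary endpoints are unaffected. This is a cheap improvement.

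**What to change.** State the precedence in SAP 5.3.1.3:

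- On any day with an answered diary antipyretic item, the diary decides, at least wherever the medication record has missing or imputed dates or an as-needed regimen.
- On days without a diary answer, use the medication record with the present date rules.
- Say explicitly which source prevails for a fully dated record of scheduled daily dosing when the diary reports no use, so that no case is left open.
- Keep the current either-source derivation as a sensitivity analysis, and tabulate by arm the subjects and days on which the sources disagree.

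The cost is SAP wording and programming, since both sources are already collected. The derivation must be able to tell a diary answer of no use from an unanswered item; the SAP does not list the response options. The downside is reliance on the subject's daily report when the two sources disagree, which the retained sensitivity analysis makes visible.

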5.3.1.4. Viral kinetics

The viral culture (TCID₅₀) measurements are analyzed using two methods (depending on influenza subtype); ie, NP ELISA and Hemagglutination Inhibition Assay. For analysis purposes the results from the NP ELISA method will be used when available, otherwise the results from the Hemagglutination Inhibition Assay will be used. This will be determined per analysis visit. As a consequence, the series of results of a subject can be a combination of both methods (for example at baseline the NP ELISA result is used and at Day 3 the Hemagglutination Inhibition Assay result is used).

The endpoints listed below will be based on results from nasal mid-turbinate (MT) swabs taken from central testing, excluding data from leftover samples from local virology tests.

Measurement	Formula
Log ₁₀ viral load actual values (Log ₁₀ vp/mL)	Log ₁₀ of the actual values as measured with qRT PCR
Viral load negativity (Log ₁₀ vp/mL)	Viral load will be categorized as Negative or Positive: 
 • Negative (lower than LOD) • Positive (between LOD and LOQ or quantifiable (above LOQ)).
Viral load categorization (Log ₁₀ vp/mL)	Viral load will be categorized as Target not detected, Target detected, and Quantifiable: 
 • Target not detected (lower than LOD) • Target detected (between LOD and LOQ) • Quantifiable (above LOQ)
Log ₁₀ viral load change from baseline (Log ₁₀ vp/mL)	Log ₁₀ viral load post-baseline value – log ₁₀ viral load baseline value

Log ₁₀ viral titer actual values (Log ₁₀ TCID ₅₀ /mL)	Log ₁₀ of the actual values as measured with viral culture
Viral titer negativity (Log ₁₀ TCID ₅₀ /mL)	Viral titer will be categorized as Negative or Positive: 
 • Negative (lower than LOQ) • Positive (quantifiable results)
Log ₁₀ viral titer change from baseline (Log ₁₀ TCID ₅₀ /mL)	Log ₁₀ viral titer post-baseline value – log ₁₀ viral titer baseline value
Viral load AUC _{0-10d} trapezoidal method	
Viral load AUC calculated from baseline to Day 10:
 
AUC is calculated by the trapezoidal summation rule, based on planned days of sampling, including the timepoints with (imputed) values available:
 $\text{Sum over } i \text{ of } (t_{i+1}-t_i) * (\text{Viral load}_{i+1} + \text{Viral load}_i) / 2$ 
The following rules will be applied in the order described below to deal with missing values before calculating the Viral load AUC:
 
 • If the baseline value is missing, then the mean baseline value over all subjects in the ITT-i set will be used. • If a single or sequential intermediate values (not the baseline value) are missing, then the missing value will be replaced by linear interpolation of the two adjacent values. Note: this is done automatically when applying the trapezoidal summation rule. If the Day 10 value is missing, but there is an assessment after Day 10, then this value will be used to interpolate the value for Day 10. • If the Day 10 value is missing, and there are no values available after Day 10, then it will be imputed with the last observed post-baseline value (LOCF). 
Note: In case no post baseline value is available the AUC will be missing.

Viral titer AUC _{0-10d} trapezoidal method	
Viral titer AUC calculated from baseline to Day 10:
 
AUC is calculated by the trapezoidal summation rule, based on planned days of sampling, including the timepoints with (imputed) values available:
 $\text{Sum over } i \text{ of } (t_{i+1}-t_i) * (\text{Viral titer}_{i+1} + \text{Viral titer}_i) / 2$

	
The following rules will be applied in the order described below to deal with missing values before calculating the Viral titer AUC:
 
 • If the baseline value is missing, then the mean baseline value over all subjects in the ITT-i set will be used. • If a single or sequential intermediate values (not the baseline value) are missing, then the missing value will be replaced by linear interpolation of the two adjacent values. Note: this is done automatically when applying the trapezoidal summation rule. If the Day 10 value is missing, but there is an assessment after Day 10, then this value will be used to interpolate the value for Day 10. • If the Day 10 value is missing, and there are no values available after Day 10, then it will be imputed with the last observed post-baseline value (LOCF). 
Note: In case no post baseline value is available the AUC will be missing.

Time to viral negativity by qRT-PCR (days) [Time-to event]
	
The time to viral negativity is defined as the time (in days) from first study drug intake until a subject is considered influenza A viral negative. This is the first timepoint of two consecutive timepoints with confirmed negative nasal MT swab ie, the first and next assessment are equal to 'negative' (ignoring missing values). In case the first 'negative' is the last available assessment the subject is considered to have reached viral negativity at this last assessment. If this doesn't occur, a subject will be censored at the time of the last observed non-negative swab + 1 day. Note that for deriving the time to viral negativity by qRT-PCR every subject is considered positive at baseline.

Time to viral negativity by viral culture (days) [Time-to event]
	
The algorithm for Time to viral negativity by viral titer is similar as 'Time to viral negativity by viral load' but viral titer assessments are used instead.

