- There was an estimated reduction in time to resolution of the 7 primary influenza symptoms vs placebo of 13% and 17% for the pimodivir 600 mg bid and pimodivir 600 mg bid + OST 75 mg bid treatment groups, respectively, and an estimated increase in time to resolution of the influenza symptoms vs placebo of 7% for the pimodivir 300 mg bid treatment group. The differences in time to resolution compared to placebo treatment were not statistically significant for active treatment groups. However, given that the study was finalized at the interim analysis for early success on virologic response, the sample sizes per arm were relatively small, and clinical outcome comparisons had reduced power to show differences.

In Study 63623872FLZ2002 (hospital study), adult (aged 18 to ≤64 years) and elderly (aged 65 to ≤85 years) hospitalized subjects with influenza A infection received pimodivir 600 mg bid + OST 75 mg bid or pimodivir placebo bid + OST 75 mg bid, for a total of 7 days. The following results were observed:

- **Viral Kinetics**
  - The difference (95% CI) in viral titer (by culture) AUC of pimodivir 600 mg bid + OST 75 mg bid treatment vs placebo bid + OST 75 mg bid treatment

was  $-0.5$  ( $-2.0, 1.0$ )  $\log_{10}$  TCID50/mL\*day. For subjects that were treated within 72 hours from onset of symptoms, the difference (95% CI) in AUC was  $-1.2$  ( $-4.2, 1.8$ )  $\log_{10}$  TCID50/mL\*day. For subjects that were treated within 96 hours from onset of symptoms, the difference (95% CI) in AUC was  $-0.9$  ( $-3.0, 1.3$ )  $\log_{10}$  TCID50/mL\*day.

- Based on viral titer (by culture), the median time to viral negativity was 1.1 and 1.3 days for the pimodivir 600 mg bid + OST 75 mg bid and placebo bid + OST 75 mg bid treatment groups, respectively, as estimated from an accelerated failure time model. For subjects that were treated within 72 hours from onset of symptoms, the median time to viral negativity was 1.2 and 1.8 days for the pimodivir 600 mg bid + OST 75 mg bid and placebo bid + OST 75 mg bid treatment groups, respectively, as estimated via the accelerated failure time analysis. For subjects that were treated within 96 hours from onset of symptoms, the median time to viral negativity was 1.2 and 1.6 days for the pimodivir 600 mg bid + OST 75 mg bid and placebo bid + OST 75 mg bid treatment groups, respectively, as estimated via the accelerated failure time analysis.

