1.1. Trial Objectives

Primary Objective

The primary objective is to evaluate superiority of pimodivir in combination with standard-of-care (SOC) treatment compared to placebo in combination with SOC treatment, with respect to the time to resolution of influenza-related symptoms.

Secondary Objectives

The secondary objectives are:

- To investigate the safety and tolerability of pimodivir in combination with SOC treatment compared to placebo in combination with SOC treatment.
- To evaluate superiority with respect to the hospital admission rate 28 days after initiation of treatment in the pimodivir in combination with SOC treatment arm, compared to the placebo in combination with SOC treatment arm.
- To evaluate superiority with respect to the incidence of complications associated with influenza after the start of study treatment in the pimodivir in combination with SOC treatment arm, compared to the placebo in combination with SOC treatment arm.
- To investigate time to resolution of each of the 10 individual influenza-related symptoms as assessed by the PRO measure Flu-iiQ™.
- To investigate the time to return to daily activities as assessed by the subject in the pimodivir in combination with SOC treatment arm, compared to the placebo in combination with SOC treatment arm.
- To investigate the time to resolution of fever in the pimodivir in combination with SOC treatment arm, compared to the placebo in combination with SOC treatment arm.
- To investigate all-cause mortality in the pimodivir in combination with SOC treatment arm, compared to the placebo in combination with SOC treatment arm.
- To assess the pharmacokinetics (PK) of pimodivir and to explore the PK/pharmacodynamic (PD) relationships of pimodivir for efficacy and safety.
- To investigate the acceptability (taste and swallowability) of the pimodivir formulation in adolescents.

- To investigate the emergence of viral resistance against pimodivir detected by genotyping and/or phenotyping.
- To evaluate superiority with respect to time to viral negativity in the pimodivir treatment arm compared to the control arm by quantitative real time polymerase chain reaction (qRT-PCR) and viral culture.

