2.2.2. Efficacy Analysis Sets

Efficacy will be analyzed on the intent-to-treat infected (ITT-i) set and by randomized treatment. The primary efficacy endpoint will also be analyzed on the Per Protocol set. The primary efficacy endpoint and the two most important secondary endpoints (ie, 'Incidence of treatment-emergent adjudicated influenza complications' and 'Incidence of hospital admission 28 days after treatment initiation') will also be analyzed on the intent-to-treat non-infected (ITT-ni) set and by randomized treatment.

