4.1. Demographics and Baseline Characteristics

Demographics and baseline disease characteristics will also be done on the PP and ITT-ni sets.

Descriptive statistics or frequency tabulation will be provided for the following parameters.

- Demographic parameters:
 - Sex (Male, Female)
 - Race (White, Black or African American, Asian, American Indian or Alaska Native, Native Hawaiian or Other Pacific Islander, Multiple). The specification of the category 'Multiple' will only be listed. The 'Not reported' category will not be added for the denominator.
 - Ethnicity (Hispanic or Latino, Not Hispanic or Latino)
 - Country
 - Geographic region (Based on country according to UN classification of Geographic regions^[5]: Europe/Africa, Northern-America, Latin America and the Caribbean, Asia and Oceania)
 - Age (years and categories: 13-17 years [≥ 13 - < 18], 18-65 years [≥ 18 - ≤ 65], 66-85 years [> 65 - ≤ 85])
 - Age (years and categories: Adolescents (12-17 years) [≥ 12 - ≤ 17], Adults (18-64 years) [≥ 18 - ≤ 64], From 65 to 84 years [≥ 65 - ≤ 84], 85 years and over [≥ 85])
 - Weight at baseline (kg)
 - Height at baseline (cm)
 - BMI at baseline = Weight at baseline (kg) / (Height at baseline (m))² (rounded to 1 decimal. Although available in the raw data, BMI will be recalculated from last weight and height measurement before start of treatment)
 - Current Tobacco use: tobacco, cigarettes, cigars, patches/gum, pipes, E-cigarettes or equivalent, smokeless tobacco (Yes, No, Missing) Note that 'No' also includes ex-smokers
 - Childbearing potential (only listed)

- Baseline disease characteristics:
 - Influenza A subtype category (A/H1N1, A/H3N2, other)
 - Baseline influenza A viral load (log₁₀ vp/mL), assessed by qRT-PCR
 - Baseline influenza A viral titer (log₁₀ TCID₅₀/mL) assessed by viral culture
 - Broad respiratory panel (show the reported pathogen)
 - Baseline composite symptom score of 10 influenza-related symptoms
 - Return to daily activities questionnaire baseline category

- Patient Global Impression of Severity of Influenza symptoms at baseline
- EQ-5D VAS at baseline
- EQ-5D Valuation index at baseline
- Respiration rate at baseline (breaths/min)
- Heart rate (beats/min)
- Temperature (°C) at baseline
- qRT-PCR negativity at baseline
- Viral culture negativity at baseline
- Time since onset of influenza symptoms, as randomized (≤ 48 hours, > 48 hours)

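### Time to viral negativity by culture has no rule for subjects already culture-negative at baseline, which dilutes the treatment comparison on a secondary superiority objective by an amount the documents do not allow one to fix

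*SAP*

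**What the plan says.** - **Objective.** SAP 1.1 lists among the secondary objectives "To evaluate superiority with respect to time to viral negativity in the pimodivir treatment arm compared to the control arm", by qRT-PCR and by viral culture. The endpoint is outside the three-endpoint hierarchy of SAP 5.1.1, and no power is stated for it.
- **Analysis set.** SAP 2.2.2: "Efficacy will be analyzed on the intent-to-treat infected (ITT-i) set and by randomized treatment". SAP 2.2.2.1 defines infection by central PCR results alone. Culture positivity is not required, and a subject without a positive baseline PCR can enter on two positive post-baseline results.
- **Event.** SAP 5.3.1.4, for qRT-PCR: "This is the first timepoint of two consecutive timepoints with confirmed negative nasal MT swab". A single negative also counts if it is the last available assessment.
- **Baseline convention.** In the same entry: "Note that for deriving the time to viral negativity by qRT-PCR every subject is considered positive at baseline". It names qRT-PCR only.
- **Culture.** "The algorithm for Time to viral negativity by viral titer is similar as" the viral-load version, and nothing is said about baseline status.
- **Such subjects are foreseen.** SAP 4.1 tabulates "Viral culture negativity at baseline".
- **Tests.** SAP 5.3.2 applies stratified Gehan-Wilcoxon and log-rank tests. SAP 5.3.2.4 adds baseline titer as a covariate, but only in the AFT and Cox models.
- **Contrast.** For time to resolution of fever, SAP 5.3.2.3 adds an analysis of subjects with fever at baseline.

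**The concern.** A subject whose culture is negative at baseline and stays negative has nothing to clear, yet enters the analysis as an early event. There are two readings of the definition, and each has a defect.

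1. The qRT-PCR convention carries over. The event then falls at the first post-baseline swab, Day 3, whatever the arm.
2. It does not carry over. The first of the two consecutive negatives is then the baseline swab, which is taken before dosing. The event time is zero or negative, apart from a swab taken within the 30-minute allowance of SAP 2.5. The AFT families in SAP 5.3.2 (lognormal, log-logistic, Weibull) work on log time and cannot use such a value.

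Two programmers could therefore derive different datasets from the same text. On either reading these subjects carry no information about clearance and draw the two curves together. What is at stake is the sensitivity and interpretability of the culture result.

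**Working it through.** **1. The plan's own figure.** None exists for this endpoint. As a check on the test code, 10,000 simulated trials with 300 subjects per arm gave Gehan-Wilcoxon powers of 97.4, 93.4, 94.0 and 88.6% for the four scenarios of SAP Table 2. The stated values are 97.3, 93.3, 93.7 and 88.3%.

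**2. Inputs from the documents.**
- 600 confirmed-infected subjects, 1:1, one-sided 0.025 (SAP 1.4).
- Swabs on Days 3, 6, 10 and 14 (Time and Events Schedule). Day 1 is the day of first intake (SAP 2.4), so these fall about 2, 5, 9 and 13 days after first dose.

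**3. Assumptions.**
- Log-logistic time to culture negativity in culture-positives, scale s = 0.55, and a 25% reduction. The documents give these values for the primary endpoint, not for this one.
- Placebo median m among culture-positives: 1.3 to 5 days. The only culture medians in the documents are from the hospital study (Protocol 1.1, Clinical Efficacy): "the median time to viral negativity was 1.1 and 1.3 days" overall (pimodivir, placebo), and 1.2 and 1.8 days in subjects treated within 72 hours of onset.
- Baseline culture-negative share f: 10 to 30%. The documents give none.

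**4. Why the difference shrinks.** If all baseline-negatives stay negative and f is equal in the arms, the share negative by time t is F_all(t) = f + (1 − f)·F_pos(t). The arm difference is then multiplied by (1 − f). With F_pos(t) = 1/(1 + (t/m)^(−1/s)) at the Day 3 swab (t = 2):
- m = 5: placebo 15.9%, pimodivir (m = 3.75) 24.2%, difference 8.3 points. With f = 30% the shares are 41.1% and 46.9%, difference 0.7 × 8.3 = 5.8 points.
- m = 1.3: placebo 68.6%, pimodivir (m = 0.975) 78.7%. Most culture-positives are already negative at that swab, so the extra early events add little noise.

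**5. Power.** Simulated times are m·exp(s·ε), with ε standard logistic, and are multiplied by 0.75 on pimodivir. Each is observed at the first of 2, 5, 9 or 13 days, otherwise censored. The test is the unstratified tie-corrected rank-sum test, equivalent to Gehan-Wilcoxon when the only censoring is at a common time. There were 3,000 trials per cell, with a simulation error of about 0.8 points at 75% power. Entries are power with all ITT-i → baseline culture-positives only, when all baseline-negatives stay negative.

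| Placebo median | f = 10% | f = 20% | f = 30% |
|---|---|---|---|
| 1.3 d | 74.4 → 75.4 | 67.9 → 70.3 | 61.0 → 65.9 |
| 1.8 d | 83.0 → 85.0 | 77.7 → 82.5 | 68.2 → 75.5 |
| 3.5 d | 87.8 → 91.3 | 77.3 → 88.8 | 63.6 → 82.6 |
| 5 d | 85.4 → 91.4 | 73.5 → 88.3 | 59.0 → 84.5 |

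Allowing for simulation error and small changes of setting (for example scale 0.5), the loss is about 1-9 points at 1.3-1.8 days and about 2-27 points at 3.5-5 days.

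**6. If half of the baseline-negatives are culture-positive later** and behave like the other positives (an assumption), with f = 30%:
- 1.3 d: 72.4 → 66.2
- 1.8 d: 82.2 → 77.4
- 3.5 d: 82.4 → 83.0
- 5 d: 80.3 → 83.8

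Restriction then costs power at short medians and gains little at long ones.

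**7. Other checks** (2,000 trials per cell, all baseline-negatives staying negative). The log-rank loss is smaller: at a 3-day median and f = 20% it is 75% → 81%, against 78% → 87% for Gehan-Wilcoxon. With an 18% reduction at the same median and share, Gehan-Wilcoxon is 48% → 59%. Type I error is near 2.5% one-sided either way.

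**The case against.** - **The only culture medians in the documents are short**, and there the loss is small. This stands as a reason to quote the low range as well as the high one. Those medians come from hospitalised subjects and may themselves include baseline-negatives, so they do not settle the matter.
- **One negative swab is not proof of no virus.** The assay has a detection limit (0.75 log10, SAP 5.1.2), and the event generally needs two consecutive negatives. A subject negative at baseline may be positive on Day 3 and is then informative. This stands. A reader might infer that restricting to baseline-positives always gains power despite fewer subjects; step 6 shows that it need not.
- **Baseline titer is already handled in part.** The AFT and Cox models adjust for it, and the repeated-measures model of titer uses it. Adjustment may recover some of the loss in those models; how much is not established here. It does not reach the Gehan-Wilcoxon or log-rank tests.
- **Protocol 11.1 places the efficacy endpoints on ITT-i.** This stands against replacing the ITT-i analysis, not against adding to it.
- **The endpoint is outside the hierarchy.** True, and it limits the importance of the point.

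**Conclusion.** The gap is real. The culture endpoint lacks an at-risk or event-time rule for subjects whom the SAP itself expects, and one reading yields event times that the AFT model cannot use. Where baseline-negatives stay negative, the rank-test comparison is diluted in expectation. The size can only be ranged, because the share of such subjects, the median among culture-positives and the chance of later positivity are all assumptions.

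Three stronger inferences are not supported:
- That the early events are identical in the two arms. Baseline status precedes treatment, so they are balanced by randomisation only on average.
- That the result is biased towards a false claim. Type I error is unchanged, and neither the primary endpoint nor the hierarchy is touched.
- That a large loss is established. The upper end of the range needs medians well above any culture median in the documents, together with baseline-negatives who all stay negative.

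**What to change.** In SAP 5.3.1.4 and 5.3.2.4:

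(a) State the event-time rule for subjects culture-negative at baseline, with no event before the first post-baseline swab. State also how a missing baseline titer is handled.

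(b) Keep the protocol's ITT-i analysis and add an analysis of time to culture negativity in ITT-i subjects with a quantifiable baseline titer, in the way already planned for baseline fever. Report the number excluded per arm.

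The subset is defined before treatment, so the randomised comparison is preserved, and no new data are needed. The cost is fewer subjects in the added analysis and one more table.
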